5.6.2 HANDLING OF PARTICIPANT WITHDRAWALS OR TERMINATION

Upon withdrawal, the subject and physician may elect to have an implanted device explanted. If the device is explanted, the subject should continue to be followed at least through 3 months post-explant or until the wound is healed, whichever is longer.

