5.7 PREMATURE TERMINATION OR SUSPENSION OF STUDY

In the event of premature termination or suspension of the study, the Sponsor will promptly notify the investigational center and communicate a plan for orderly termination or suspension. Elective explants of implanted devices shall be performed under this protocol, prior to study close-out.

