The Sponsor and linvestigator will distinguish between the serious adverse events related to the investigational device and those related to the procedures (any procedure specific to the clinical investigation). An adverse event can be related both to procedures and the investigational device. Complications of procedures are considered not related if the said procedures would have been applied to the patients also in the absence of investigational device use/application.

Related to Device - Events reasonably anticipated to be related to the physical presence of the device, e.g. erosion, a device deficiency, dislodgment.

Related to Procedure — Events reasonably anticipated to be related to procedures (pertaining to implant) described in this protocol.

NOTE: Procedure related events refers to the procedure related to the initial application of the investigational medical device only and therefore not to any other procedures or treatments applied later throughout the clinical investigation, for instance to treat (serious) adverse events.

In some particular cases the event may be not adequately assessed because information is insufficient or contradictory and/or the data cannot be verified or supplemented. The Ssponsor and the Investigators will make the maximum effort to define and categorize the event and avoid these situations. Where the Sponsor remains uncertain about classifying the serious event, it should not exclude the relatedness and classify the event as "possible".

Particular attention shall be given to the causality evaluation of unanticipated serious adverse (device) events. The occurrence of unanticipated events related to the use of the device (USADE) could suggest that the clinical investigation places subjects at increased risk of harm than was to be expected beforehand.

All AEs will be collected from the time of informed consent through the end of the study. Death should not be recorded as a separate adverse event, but rather as an outcome of the specific SAE which led to the subject's death. Adverse Events that would be reasonably expected to be associated with any surgical procedure (e.g.: anesthesia associated nausea, surgical site pain) will not be categorized as procedure or device related in the 30 days post the surgical procedure.

Notes:

- 1. Any current condition that is recorded as a pre-existing condition is not an AE, unless there is a worsening of that condition in terms of nature, severity, or degree of incidence.

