8.7 STUDY HALTING RULES

There are no statistically-based rules related to early trial termination. However, if two of the first five subjects experience a serious device or procedure related adverse event, or if three total subjects experience a serious device or procedure related adverse event, the study will be halted until the time an acceptable (to FDA and sponsor) mitigation can be implemented. If no such mitigation is possible, the study will be terminated. In addition, the Sponsor and independent Medical Director will review safety data every two months, including the emergence of serious adverse events and unanticipated adverse device effects, and will convene a special session of the DSMB if the observed risks appear greater than expected, even if the stopping rule is not met.

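### The note on procedure-related events in Protocol 8.2.1 can keep a serious complication of BGI explant surgery out of the 8.7 halting count, in a narrow set of cases

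*Protocol*

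**What the plan says.** **The count.** Protocol 8.7 sets two triggers: two of the first five subjects, or three in total, with a serious event related to the device or procedure. On the second, "if three total subjects experience a serious device or procedure related adverse event, the study will be halted until the time an acceptable" mitigation is in place, acceptable to FDA and the sponsor. Section 8.7 gives no definition of relatedness.

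**The definitions.** These are in Protocol 8.2.1.
- Related to device: events tied to the physical presence of the device.
- Related to procedure: "Events reasonably anticipated to be related to procedures (pertaining to implant) described in this protocol".
- A note then narrows the second term: "Procedure related events refers to the procedure related to the initial application of the investigational medical device only", and "not to any other procedures or treatments applied later throughout the clinical investigation".
- The same section separates device-related serious events from "those related to the procedures (any procedure specific to the clinical investigation").

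**Explant.** The protocol plans for removal in several places. Section 5.6.2: "Upon withdrawal, the subject and physician may elect to have an implanted device explanted". Section 7.3.4 lists signs that call for explant, among them persistent discomfort, and adds any situation where the ophthalmologist expects benefit. Section 7.3.2 gives removal as the remedy for persistent hypotony. Section 5.7 covers elective explants when the study is terminated or suspended.

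**The concern.** Removal is surgery that a subject undergoes only because the device was implanted. A serious injury during it bears on whether the study should go on. Under the note, that injury is not procedure related, because the operation came later. It is device related only if an assessor ties it to the device, and the device definition looks to physical presence, which does not clearly cover injury caused by taking the device out.

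Section 8.7 is the only rule that makes a halt mandatory and requires a mitigation acceptable to FDA. During accrual, a missed count lets further eyes be implanted. After accrual, expected to take one to three months (Protocol 1), what is lost is mainly the required mitigation, such as a changed explant technique for subjects still carrying a device through 24 months.

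**Working it through.** The plan states no operating characteristic for the halting rule, so there is no figure to reproduce. The check is first textual, then a count.

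**Step 1. Two lines of 8.2.1 point in opposite directions.** The wording on any procedure specific to the investigation brings explant in. So does the rule that procedure complications are unrelated if the procedure would have been done without the device: an explant could not have been. The definition tied to implant and the note take explant out, and the note does so expressly. An assessor who follows the note has a clear basis for not counting.

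**Step 2. Ways a subject with an explant complication would still count.**
- An earlier serious device event already counts the subject. Hypotony or infection that needs surgery to prevent permanent impairment can itself be serious (8.1.2).
- Outcomes that worsen in sequence are reported as one event, the worst (8.1.1).
- The adverse device effect definition covers use of the device and inadequate implantation (8.1.3).
- Removal because of malfunction is device related (8.2.1, notes).
- Where the relationship is weak but cannot be ruled out, or cannot be assessed, the event is rated possible. For a serious event on which the sponsor stays uncertain, "it should not exclude the relatedness and classify the event as" possible (8.2.1).

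**Step 3. What is left.** A serious operative complication of an explant done on withdrawal (5.6.2) or for a non-serious sign (7.3.4), in a subject with no earlier countable event, judged not even possibly device related. A second implant (8.5) is arguable, because first application can be read per device.

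**Step 4. A fixed case.** Two subjects are already counted, not both among the first five. A third has the complication in step 3.
- Under the note: count = 2, no halt.
- If explant surgery counts: count = 2 + 1 = 3, halt.

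**Step 5. Illustration with assumed rates.** None of these rates is in the documents. Let p = 0.10 be the chance that a subject has a countable event from the first implant or the device, s the share with later BGI surgery, q the chance of a serious operative complication given that surgery, and c the share of such complications counted anyway. Ten independent subjects, full follow-up.

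- All later surgery counts: x = 1 − (1 − p)(1 − s·q).
- Under the note: x = 1 − (1 − p)(1 − s·q·c).
- P(halt) = 1 − [P(0 of first 5)·P(at most 2 of last 5) + P(1 of first 5)·P(at most 1 of last 5)].

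Middle case, s = 0.30 and q = 0.10:
- All counts: x = 1 − 0.90 × 0.97 = 0.127. P(halt) = 1 − (0.5071 × 0.9832 + 0.3688 × 0.8759) = 0.178.
- Note with c = 0: x = 0.10. P(halt) = 1 − (0.5905 × 0.9914 + 0.3281 × 0.9185) = 0.113.

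| s, q | P(halt), all count | Gap, c = 0 | Gap, c = 0.50 | Gap, c = 0.75 | Gap, c = 0.90 |
|---|---|---|---|---|---|
| 0.20, 0.05 | 13.4% | 2.0 | 1.0 | 0.5 | 0.2 |
| 0.30, 0.10 | 17.8% | 6.5 | 3.4 | 1.7 | 0.7 |
| 0.50, 0.20 | 35.9% | 24.6 | 13.2 | 6.7 | 2.7 |

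Gaps are in percentage points. Step 2 rules out c = 0 as a realistic value, so that column is only a ceiling. Independence inflates every gap, because the device events that prompt an explant often count the subject already.

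**The case against.** The strongest reply is that almost nothing falls through. The indications that make removal important, such as hypotony and infection, will usually have counted the subject before the explant. Elective explants under 5.7 add little: "Elective explants of implanted devices shall be performed under this protocol, prior to study close-out" applies only once the study is being terminated or suspended. An injury while extracting the device is hard to rate below possible. Section 8.7 also provides for events outside the count: the sponsor and independent Medical Director review safety every two months and must convene the DSMB if risks appear greater than expected. The DSMB meets at least quarterly and can recommend termination (8.8). SAEs reach the sponsor within three working days (8.4.2), and the IRB can suspend the trial (12.1). With short accrual, most explants would follow the last implant.

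Most of this stands, and it limits the point to the cases in step 3. It does not remove them. The default to possible helps only when the assessor is uncertain; one who applies the note and the physical-presence definition with confidence may leave the event out. The reviews depend on judgement and do not set the 8.7 count.

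A reader might infer that the halting rule ignores explant harm in general, or that the note costs up to 24.6 points of halting probability. The documents support neither. The routes in step 2 capture most such subjects, and the 24.6 figure needs assumed rates at their high end with no complication counted by any other route.

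**Conclusion.** The gap is real on the text but narrow. A serious operative complication of an explant on withdrawal or for a non-serious sign can be left out of both triggers, provided the subject has no earlier countable event and the complication is judged not even possibly device related. How often this would happen cannot be estimated from the documents, and the table in the working does not carry the conclusion. What does is the size of the thresholds: with two and three subjects, one omission can change the result. That justifies a small repair to a mandatory safety rule. It does not show that safety oversight in the study is inadequate.

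**What to change.** Keep the note in 8.2.1 for routine classification and add one sentence to Protocol 8.7:

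*For both triggers, a serious adverse event related to any BGI surgery under this protocol (first implant, explant, revision or second implant) counts as procedure related, regardless of the NOTE in 8.2.1.*

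Have the investigator and the sponsor record relatedness to that surgery for each SAE. This must be asked for explicitly: the Explantation form items described in Protocol 2.3.3 are ease of explant and device intactness, and the note means relatedness to explant surgery need not otherwise be coded.

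Cost: one extra causality judgement per SAE after later BGI surgery, with no added visits. A halt becomes slightly more likely. The term procedure related will be wider in 8.7 than in 8.2.1, so the sentence should name the note it overrides, as above.

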8.8 SAFETY OVERSIGHT

A Data Safety Monitoring Board (DSMB) will be assembled to routinely monitor ongoing safety of trial participants. The DSMB will meet at least quarterly and, upon data review, make recommendations to the sponsor to:

- Continue the trial as planned
- Continue the trial with modification(s), or
- Terminate the trial due to safety concerns.

A DSMB charter will be developed separately in a cooperative effort between sponsor and the DSMB.

9 CLINICAL MONITORING

It is the responsibility of the Sponsor to ensure proper monitoring of the study per regulations. Appropriately trained Sponsor personnel or delegates appointed by the Sponsor will perform study monitoring at the investigation site in order to ensure that the study is conducted in accordance with the CIP, the signed Clinical Trial Agreement, and applicable regulatory requirements. The Sponsor must therefore be allowed access to the Subjects' clinic and hospital records when so requested as per the consent form, Privacy Authorization (US only) and Clinical Trial Agreement.

Procedures required in this CIP require source document verification for this study. A separate Monitoring Plan will detail levels of source verification for this study. Monitoring visits will be conducted periodically to assess study progress, the Investigator's adherence to the CIP and regulatory compliance. This includes but is not limited to IRB/EC approval and review of the study, maintenance of records and reports, review of the consent process and review of source documents against Subject case report forms to ensure data points are correct and that adverse events are being reported.

Monitors facilitate site regulatory and study compliance by identifying findings of non-compliance and communicating those findings along with recommendations for preventative/corrective actions to site personnel. Communication with the site personnel occurs during the visit and following the visit via a written follow-up letter. Monitors may work with study personnel to determine appropriate corrective action recommendations and to identify trends within the study or at a particular center.

Frequency of monitoring visits will occur based on subject enrollment, timing of the study visits, duration of the study, study compliance, findings from previous monitoring visits and any suspected inconsistency in data that requires investigation. All active sites will have a closure visit. A closure visit is a visit that occurs after a site's last required follow-up visit. Closure visit activities may include source verification of the data and closure of any findings and/or study-related activities. Storage and accountability of investigational product used for this study will be assessed and monitored throughout the study at each site.

10 STATISTICAL CONSIDERATIONS

10.1 STATISTICAL AND ANALYTICAL PLANS

Because this is a first-in-human feasibility study, no formal Statistical Analysis Plan will be developed.

10.2 STATISTICAL HYPOTHESES

Because this is a small, unpowered, first-in-human feasibility study, no formal tests of hypothesis are planned.

10.3 ANALYSIS DATASETS

Data from all enrolled subjects for whom an implant is attempted will be included in data analysis. Certain exploratory analyses may be conducted that include only subjects who received an implant, or who have retained an implant for a minimum period of time.

10.4 DESCRIPTION OF STATISTICAL METHODS

10.4.1 GENERAL APPROACH

Because this is an unpowered feasibility study, no formal tests of hypothesis will occur. All outcome data will be summarized using appropriate descriptive statistics (e.g. mean, standard deviation and 95% confidence intervals for continuous data; frequency distributions for categorical data). Data will be summarized in a manner that will provide sufficient basis for a risk vs benefit assessment to inform considerations for future study.

10.4.2 ANALYSIS OF THE PRIMARY EFFICACY ENDPOINT(S)

The primary endpoint is a binary measure of at least 20% reduction from baseline in diurnal IOP at six months. This endpoint will be descriptively summarized as a proportion of subjects meeting this criterion, along with the corresponding 95% confidence interval.

Given the small sample size of this study, the primary efficacy endpoint will be evaluated several different ways to assess the robustness of study conclusions. One analysis will determine whether or not a subject is classified as success (at least 20% reduction in IOP) based strictly on the baseline and follow-up IOP. Another analysis will be conducted that classifies any subject as a failure if, at the time of the endpoint evaluation, the subject:

- is taking increased glaucoma medication over baseline
- has required glaucoma re-operation
- has experienced a clinically significant post-operative hypotony that results in injury (i.e., no hypotony maculopathy, astigmatism, flat anterior chamber, corneal folds, choroidal effusions, suprachoroidal hemorrhage) or requires invasive intervention
- has been unable to receive an implant
- has discontinued trial participation due to the investigational device
- requires oral or intravenous glaucoma medication
- experienced a serious device-related AE.

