4.1 All AEs and SAEs

The primary summary of safety will consist of all adverse events (AEs), adverse device effects (ADEs), serious adverse events (SAEs), and unanticipated adverse device effects (UADEs) occurring in the implanted eye through 6 months post-implant, by type, summarized by study and overall. For each reported event, the number of events (# Event), number of participants with an event (n), and the percentage of participants among the total sample size (N) will be summarized. Supportive analyses will include summaries of device-related adverse events and secondary surgical interventions through 24 months of follow-up.

Table X. Summary of Adverse Events								
Event	# Events	% (n/N) Participants						
Adverse Events								
Serious Adverse Events								
Device-Related Adverse Events Possibly Probably Definitely Procedure-Related Adverse Events Possibly Probably Definitely								
Study Device and/or Procedure Related Adverse Events								
Serious Study Device and/or Procedure Related Adverse Events								

Table X. Summary of Device-Related Adverse Events					
Participant ID (AE#)	Description of Event	# Events	% (n/N) Participants		

Table X. Summary of Secondary Surgical Interventions						
Participant ID (AE#)	Surgical Intervention	# Events	% (n/N) Participants			

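### In Protocol 10.4.2 the composite's serious-event criterion covers device-related events only, so a serious event rated procedure-related alone can still be scored a success

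*Protocol*

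**What the plan says.** Protocol 10.4.2 evaluates the primary endpoint in several ways to judge robustness. One analysis uses baseline and follow-up IOP alone. Another, called the composite here, makes a subject a failure on any of seven criteria. The criterion on serious events applies to a subject who "experienced a serious device-related AE". Three others apply to a subject who "has required glaucoma re-operation", "has experienced a clinically significant post-operative hypotony that results in injury" (or needs invasive intervention for it), or "has been unable to receive an implant". The remaining three are increased glaucoma medication, oral or intravenous glaucoma medication, and discontinuation because of the device.

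Protocol 8.2.1 has the sponsor and investigator "distinguish between the serious adverse events related to the investigational device and those related to the procedures". It describes device-related as "Events reasonably anticipated to be related to the physical presence of the device, e.g. erosion, a device deficiency, dislodgment", and procedure-related as arising from the implant procedure. An event may be both.

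Two other rules on serious events are broader. Protocol 8.7 halts the study "if two of the first five subjects experience a serious device or procedure related adverse event", or on three such subjects in total. The SAP 4.1 summary table has a row for "Serious Study Device and/or Procedure Related Adverse Events".

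**The concern.** The implant cannot be placed without the procedure, and the composite already treats a failed implantation as a treatment failure. It would be consistent to treat serious harm from that same procedure as a failure too. The criterion does not do so, and no reason is given.

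Two things follow. First, one event can count toward stopping the trial and leave its subject scored as a success. Second, a subject's composite result can turn on whether an event is labelled device, procedure or both, which is a judgement call and can be hard to make after implant surgery.

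**Working it through.** The plan gives no figure to reproduce: Protocol 10.5 states that the sample size of 10 is not statistically derived, and no test is planned. The check is mainly textual.

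**Step 1. Which criteria depend on relatedness?**

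| Criterion (Protocol 10.4.2) | Depends on relatedness? |
|---|---|
| Increased glaucoma medication | No |
| Glaucoma re-operation | No |
| Hypotony with injury or invasive intervention | No |
| No implant received | No |
| Oral or intravenous glaucoma medication | No |
| Discontinuation | Yes, device only |
| Serious adverse event | Yes, device only |

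Five of the seven apply whatever the cause.

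**Step 2. Can a serious event be procedure-only?** Yes. Protocol 8.2.1 keeps the two classes apart and allows overlap without requiring it. It confines the procedure class to the initial application of the device. It also removes complications of procedures that would have been done anyway and, for 30 days, events expected after any surgery. What remains in the class is harm from receiving this implant.

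**Step 3. Can such an event escape the other six criteria?** Take a retinal detachment, a pre-specified event in Protocol 8.1.6. If it needs surgery to prevent permanent impairment, it is serious under Protocol 8.1.2. Suppose it is rated procedure-only, the device stays in, the subject stays in the study, there is no injurious hypotony, and no glaucoma medication is added. Retinal repair is not plainly a glaucoma re-operation. No criterion is met. With at least a 20% IOP reduction, the subject is a success.

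**Step 4. Size.** With n = 10, one subject is 1/10 = 10 percentage points. Protocol 10.4.2 asks for a 95% interval without naming a method. I use the exact (Clopper-Pearson) interval, whose lower limit is the 2.5% quantile of Beta(x, n − x + 1) and whose upper limit is the 97.5% quantile of Beta(x + 1, n − x). The starting count of 8 is an assumption.

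| Composite successes | Rate | Exact 95% CI |
|---|---|---|
| 8/10, criterion as written | 80% | 44.4–97.5% |
| 7/10, one such subject failed | 70% | 34.8–93.3% |

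**Step 5. How likely is it to matter?** The documents give no event rate. Let p be the chance that a subject has such an event and is otherwise a success. The chance of at least one in ten is 1 − (1 − p)^10. For assumed p of 2%, 5%, 10% and 20% this gives 18%, 40%, 65% and 89%.

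**The case against.** The strongest reply is that the gap is narrow and nothing is hidden.

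- **Other criteria catch surgical harm.** This stands in large part. The hypotony criterion names flat anterior chamber, choroidal effusion and suprachoroidal hemorrhage, and Step 1 shows five criteria that ignore relatedness. A reader might infer that the composite as a whole counts only device-related harm. It does not; only the serious-event and discontinuation criteria are limited in that way.
- **Device-related can be read broadly.** Protocol 8.1.3 includes events from inadequate implantation, and 8.2.1 opens by including the surgical procedure in use of the device. It also allows dual ratings and tells the sponsor to class uncertain serious events as possible. Much implantation harm may therefore be caught. But 8.2.1 still permits a procedure-only rating, so the result depends on the label.
- **Endophthalmitis looks like the obvious example, but is a weak one.** Protocol 7.3.1 links infection to the device's external communication, 7.3.4 lists clinically significant infection among the signs for explantation, and SAP 3 makes any explanted subject a failure.
- **A halting rule and an efficacy sensitivity analysis need not match.** True in principle. The case for aligning them is that the composite already brings the implantation attempt into its definition of failure.
- **Serious events are reported anyway.** This stands: Protocol 10.4.4 summarises them by relatedness and seriousness, Protocol 10.4.9 lists them by subject, and SAP 4.1 has the combined row.
- **SAP version 2.0 does not carry the composite.** Also true; its stated failure rule is explant. It does not withdraw the protocol's analysis, so Protocol 10.4.2 remains the only definition.

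**Conclusion.** The point holds for the serious-event criterion. It is narrower than the halting rule and the SAP safety table, and a subject with a serious procedure-only event outside the other six criteria can be a composite success. Each such subject is worth 10 points at n = 10. The 8/10 start and the event rates above are assumptions. The practical weight is small: this is one descriptive sensitivity analysis in an unpowered study, and its readers will see the serious events elsewhere.

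Three stronger readings are not supported.

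- A reader might multiply three halting events by 10 points and speak of 30 points of false success. That needs all three to be procedure-only, to escape six other criteria and to occur in IOP responders, with a denominator of 10 in a trial that had been halted.
- A reader might infer that the most likely early serious harms are left out. The documents give no rates. Protocol 2.3.4 names infection and hypotony as perhaps the most serious risks, and hypotony has its own criterion.
- A reader might think the discontinuation criterion needs the same change. A subject who leaves before six months has no six-month IOP, and no stated rule would turn that subject into a success.

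**What to change.** In Protocol 10.4.2, extend the serious-event criterion so that a subject fails after a serious adverse event related to the device **or the procedure**, rated under Protocol 8.2.1. Leave the other six criteria as they are. If the composite is reported alongside the explant-failure analysis in SAP 3, use the same wording there.

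The cost is one phrase. No new data are needed, because both relatedness ratings are already collected. The only downside for the sponsor is that the composite responder rate can stay equal or fall, but cannot rise.
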